4 MILESTONES

Milestone	Planned Date
Registration in the HMA-EMA Catalogue of Real-World Data	04Oct2022 (Actual)
Start of data collection	26Oct2021 (Actual)
End of data collection	3Q2024
Final report of study results	1Q2025

PRODUCT: V501/V503	PROTOCOL/AMENDMENT VERSION NO.: V503-088-01-v1
REVOPS ID NO: NIS009722	CORE DRC APPROVAL DATE: 18JUL2024
EPIDEMIOLOGY NO.(PE STUDIES ONLY): EP08039.017	

5 RATIONALE AND BACKGROUND

Background

Recurrent respiratory papillomatosis (RRP) is a generally benign, self-limiting disease, characterized by the appearance of papillomatous lesions anywhere in the aero-digestive tract; however, the vast majority of lesions (>95%) are detected in the larynx [1] [2]. Most RRP cases (>90%) are caused by HPV types 6 and 11[1]. Despite being rare, the health and economic burden associated with RRP is substantial. Nearly 20% of RRP patients experience aggressive disease requiring >40 lifetime procedures, and some patients may undergo >100 surgeries in their lifetime [3]. Further, malignant transformation of RRP occurs in 3 to 7% of patients [4].

Adult-onset RRP (AoRRP) is most often diagnosed between ages 20-40 years [3]. In cases of AoRRP, causal HPV infections are likely acquired through sexual behavior like other HPV related diseases [5]. The risk factors for AoRRP are only partially described and the mechanisms involved appear to be dominated by sexually acquired oral HPV infection transmitted horizontally between adults [5]. Risk factors for RRP are largely unknown. Limited number of studies evaluating AoRRP incidence have reported estimates that ranged from approximately 0.5 per 100,000 in Denmark and Norway to 1.8 per 100,000 in the US [6] [7] [8].

Juvenile-onset RRP (JoRRP) is most often diagnosed between ages 2-4 years[3]. In cases of JoRRP, the likely route of HPV transmission is from mother to child during labor. Numerous age cut points have been used to define JoRRP cases, typically ranging from 11 to 17 years. In Denmark, children born to mothers with external genital warts (EGW) were found to have ~230-fold increased risk compared to children born to mothers without genital warts [9]. Studies focused on JoRRP have reported incidence ranging from 0.2 to 4.3 per 100,000 across several countries, including Denmark, Norway, South Africa, Canada and the US[6] [8] [10] [11] [12] [13]. A recent US study focusing on JoRRP found a pre-vaccination incidence of 2 per 100,000 births in 23 US states, but this may have been an underestimation due to technical problems in case ascertainment and using national (versus state level) denominator data[14].

Given the high attribution of targeted HPV types 6 and 11, high GARDASIL/GARDASIL 9 vaccine effectiveness is expected against RRP. A recent Australian surveillance study found that the incidence rate of JoRRP declined from 0.16 per 100,000 in 2012 to 0.02 per 100,000 in 2016 (p=0.03) following introduction of an extensive GARDASIL vaccination program [15]. This program initially targeted females 12-26 years in 2007-2009, and achieved very high coverage, e.g., >85% of girls <16 years of age received at least one dose. Among 15 incident JoRRP cases observed in this study, none of the mothers of these cases received vaccination prior to pregnancy, and 20% had a maternal history of external genital warts. Further, 13/15 of the affected children were born vaginally, and all genotyped cases (n=7) were either HPV6 (n=4) or HPV11 (n=3) positive [15]. Similarly, investigators recently reported a significant decline in the incidence of JoRRP following HPV vaccine introduction in the United States, from 2 per 100,000 births (in 2004-2005 birth cohort) to 0.5 per 100,000

PRODUCT: V501/V503	PROTOCOL/AMENDMENT VERSION NO.: V503-088-01-v1
REVOPS ID NO: NIS009722	CORE DRC APPROVAL DATE: 18JUL2024
EPIDEMIOLOGY NO.(PE STUDIES ONLY): EP08039.017	

births (in 2012-2013 birth cohort), which the authors suggest is most likely due to GARDASIL vaccination[14]. No publications exist focused on the evaluation of AoRRP incidence trends in settings with early introduction of GARDASIL or GARDASIL 9.

Rationale

Despite this medical condition being rare, the health and economic burden associated with RRP is substantial due to the high number of surgeries required in management of each RRP case. During the period 2004 to 2007, the mean annual cost for managing JoRRP and AoRRP cases in the US (2010 US dollars) was estimated to be 123 million and 48 million, respectively [16]. As there is currently no cure, treatment focuses on maintaining voice quality and airway patency[17]. A similar percentage of children and adults with RRP experience aggressive disease requiring >40 lifetime procedures (19% and 17%, respectively) [3].

Due to the low incidence of JoRRP and AoRRP, it is not feasible to conduct a randomized controlled trial to evaluate the efficacy of HPV vaccination in reducing the incidence of RRP. However, an observational (real-world) study to assess whether GARDASIL/GARDASIL 9 vaccination is associated with a reduction in the risk of RRP in vaccinated compared to unvaccinated populations is feasible, especially in the Scandinavian region (Denmark, Norway, and Sweden). These countries have established comprehensive systems of registries nationwide that can be linked by a personal identification number (PIN) at an individual level within each country. These registry systems afford the opportunity to evaluate the population-based, real-world, effectiveness of GARDASIL/GARDASIL 9 against RRP with minimal biases due to completeness and representativeness of the data. The Nordic registries are a reputable and trusted source of data by regulatory authorities and other public health stakeholders. These registries have previously been used to conduct post-licensure surveillance studies of GARDASIL [18], which has been shown to be highly effective against high-grade cervical lesions and invasive cervical cancer in the real-world using Swedish and Danish registry information [19] [20] [21] [22] [23]. Also, long-term effectiveness of GARDASIL through at least 14 years has been demonstrated in an extension of the FUTURE II study based on registry information from Nordic countries, including Sweden, Denmark, and Norway[24]; this study extension was conducted as a commitment to the FDA and the EMA. Besides national registries, Sweden, Denmark, and Norway have similar demographic characteristics, universal healthcare, healthcare expenditure, and public healthcare systems [25] [26]. All three countries introduced GARDASIL in their national vaccination programs with the quadrivalent vaccine providing protection against HPV types 6 and 11 which cause RRP. Moreover, the proportion of sexually active 15-year-old girls (30-40%) [27] and the median age at initiation of sexual activity (16-17 years) [28] is similar in these three countries. These factors lead to a homogenous population regarding risk of HPV infection and related diseases and permit pooling of data across these countries to assess the effect of HPV vaccination on a rare outcome such as RRP.

Since initial licensure of GARDASIL in 2006, many countries have implemented publicly funded vaccination programs. GARDASIL was approved in October 2006 in Sweden, and the Swedish free-of-charge national HPV vaccination program (targeting all girls born 1999)

PRODUCT: V501/V503	PROTOCOL/AMENDMENT VERSION NO.: V503-088-01-v1
REVOPS ID NO: NIS009722	CORE DRC APPROVAL DATE: 18JUL2024
EPIDEMIOLOGY NO.(PE STUDIES ONLY): EP08039.017	

or later and attending the 5th or 6th grade; ages 10-12 years) was introduced in 2010. After public purchasing procedures, large-scale vaccination with high coverage of GARDASIL was achieved in 2012. Fully subsidized catch-up vaccination for girls aged 13-17 years has been available in Sweden since 2012, and partially subsidized for the same age group since 2007. In 2015, a 2-dose schedule (with doses administered 6 months apart) was recommended for females <14 years of age, and in 2020, males were included in the schoolbased national immunization program, with switch to use of GARDASIL 9 in 2020 as well. In Denmark, the earliest primary vaccination cohorts (girls 12 years of age since 2009) and catch-up cohorts (girls 13-15 years of age from 2008 to 2012) are now in their mid to late 20's. In 2012, another catch-up program (targeting females up to age 27 years) was implemented, with the oldest targeted females now being in their mid-30's. Vaccination coverage across targeted birth cohorts (1985+) in Denmark is >70%, but low (~5% to 10%) in cohorts born during the 1970s to the mid-1980s. In Norway, an organized school-based HPV vaccination program was initiated in 2009, in which girls approximately 12 years of age (i.e., attending the seventh grade) were offered GARDASIL in a three-dose schedule (until 2017). The first cohort targeted was girls born in 1997, with coverage >70%. Cervarix (recombinant HPV bivalent [types 16 and 18] vaccine) is currently used in Norway (since 2017).

Here, we propose a national, population registry-based case-control study investigating GARDASIL/GARDASIL 9 effectiveness against AoRRP. For the purpose of this proposed study, we will use the term "Gardasil" in the protocol to represent either GARDASIL (G4, quadrivalent vaccine) or GARDASIL 9 (G9, nonavalent vaccine), unless otherwise specified. Demonstration of Gardasil effectiveness against AoRRP would support the recommendation to administer vaccination to prevent a serious disease caused by HPV types 6 and 11, which is rarely fatal, but associated with high morbidity. Additionally, estimation of the annual incidence of JoRRP and AoRRP (evaluated separately) before and after Gardasil introduction would provide an ecologic perspective on the impact of Gardasil vaccination in the Nordic countries and could also help inform future studies focused on the evaluation of Gardasil effectiveness against JoRRP.

PRODUCT: V501/V503	PROTOCOL/AMENDMENT VERSION NO.: V503-088-01-v1
REVOPS ID NO: NIS009722	CORE DRC APPROVAL DATE: 18JUL2024
EPIDEMIOLOGY NO.(PE STUDIES ONLY): EP08039.017	

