2 ABSTRACT

Title	Population-based retrospective nested case-control study evaluating effectiveness of GARDASIL TM / GARDASIL TM 9 against adult-onset recurrent respiratory papillomatosis (AoRRP) in Sweden, Denmark, and Norway.
Protocol Number / Version	V503-088-01-v1
Date	18Jul2024
Author	PPD
Rationale & Background	Recurrent respiratory papillomatosis (RRP) is a medical condition where HPV types 6 and 11 cause wart-like growths in the larynx. The condition is rarely fatal but associated with high morbidity. Current treatment only offers temporary symptomatic relief. There is an expectation that HPV vaccination targeting types 6 and 11 will reduce incidence of RRP. To date, no study has evaluated the effectiveness of HPV vaccination against AoRRP. Due to the low incidence of AoRRP, a randomized controlled trial to evaluate the efficacy of HPV vaccination against RRP would be prohibitively large and complex. The comprehensive national registry systems of Sweden, Denmark, and Norway afford the opportunity to evaluate the effectiveness of GARDASIL/GARDASIL 9 in lowering the risk of AoRRP in the female population with minimal biases due to completeness and representativeness of the data.

PRODUCT: V501/V503	PROTOCOL/AMENDMENT VERSION NO.: V503-088-01-v1
REVOPS ID NO: NIS009722	CORE DRC APPROVAL DATE: 18JUL2024
EPIDEMIOLOGY NO.(PE STUDIES ONLY): EP08039.017	

Research Question(s) &	Primary Objective:
Objective(s)	To assess if the odds of AoRRP are lower among females fully vaccinated with GARDASIL/GARDASIL 9 before the age of 17 years versus those unvaccinated.
	The study success criterion requires demonstration that the odds ratio comparing unvaccinated to vaccinated females be \geq 3.0 and the lower bound of 95% CI be \geq 1.33.
	Secondary Objectives:
	1) To assess annual age-standardized incidence rates of AoRRP (ages 15-29 years) among males and females.
	2) To assess annual age-standardized incidence rates of JoRRP (ages 0-14 years) among males and females.
	Exploratory Objectives:
	To assess factors associated with risk of AoRRP.
Study Design	Population-based nested case-control study (primary objective);
	Population-based ecological study (secondary objectives)
Population	Primary objective:
	All females 15-29 years of age after 2006 and eligible for HPV vaccination at <17 years of age, i.e., birth cohorts 1990 and later.
	Secondary objective:
	All individuals (males and females) 0-29 years of age between the following calendar years and birth cohorts:

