Controls: For each case of AoRRP, 10 control subjects free of this diagnosis, at the time of the case's diagnosis, will be identified from the respective countries where cases were diagnosed. As the number of controls per case increases beyond 4, improvement in statistical power diminishes [30]. However, given that data for additional controls are readily available in this database study, 10 controls per case will be selected. Cases and controls will be matched on age (+/- 1 year) at diagnosis, calendar year, and the region where case was diagnosed. By design of the study (nested case-control), cases and controls will also be matched according to length of follow-up in the registries. Controls will be selected from the population at risk at the point in time when a case is diagnosed with RRP. All controls who met the matching criteria will be assigned a random number using SAS statistical software (SAS Institute Inc, Cary, NC) procedures. Then, 10 controls for each case will be selected at random from the pool of eligible controls. Controls will be assigned the same index date as the case to which they are matched. Figure 2 provides an example of case/control subject selection nested within population-based cohort (2006-2021) in this study.

PRODUCT: V501/V503	PROTOCOL/AMENDMENT VERSION NO.: V503-088-01-v1
REVOPS ID NO: NIS009722	CORE DRC APPROVAL DATE: 18JUL2024
EPIDEMIOLOGY NO.(PE STUDIES ONLY): EP08039.017	

Figure 2 Example of case/control subject selection nested within population-based cohort (2006-2021) in this study. Subject 1 is classified as a case without exposure to Gardasil prior to the index (diagnosis) date, and subject 2 is an eligible matched control with exposure to Gardasil prior to the index date.

Exposure assessment: The exposure of interest is GARDASIL or GARDASIL 9 vaccination prior to the index date for each case and matched controls. GARDASIL is a quadrivalent vaccine that is effective against HPV types 6/11/16/18, while GARDASIL 9 is a nonavalent vaccine that is effective against HPV types 6/11/16/18/31/33/45/52/58.

Exposure will be defined in 2 ways:

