Study power was estimated according to varying number of AoRRP cases (from 40 to 80), effect size (odds ratio from 3.0 to 4.0), and weighted female vaccination coverage (20 to 30%) with constant alpha-level of 0.05, control/case ratio of 10 in the age range of focus (Table 1). To detect a true OR of 3.0 with an overall vaccination coverage of 25% in all three countries combined, approximately 60 AoRRP cases would be needed to achieve a power of at least 80%, which would not be possible by including data from individual countries alone. Precision was also considered by specifying that the analyses for the primary objective be powered to detect an OR of at least 3.0, with a lower bound for the confidence interval of at least 1.33, which is equivalent to lower bound of 95% CI of vaccine effectiveness >25%. Preliminary estimates of vaccination coverage among females in the proposed age group (<17 years) obtained from public registries are ~20% for Sweden, ~50% for Denmark, and ~25% for Norway, and is expected to be at least 25% overall. By pooling data from Sweden, Denmark, and Norway for the primary analysis, the estimated combined number of AoRRP cases occurring after Gardasil introduction in these three countries (birth cohorts 1990+) is expected to be above 60 with >80% power assuming true odds ratio of 3.0 and 25% vaccination coverage (Table 2). Previously, individual level registry data were successfully pooled across multiple Nordic countries (Denmark, Finland, and Sweden) in a case-control study evaluating risk of male breast cancer in association with finasteride use [40].

In Sweden, Denmark and Norway, the attribution of HPV types contributing to HPV-related diseases (including RRP) is similar, and the median age of sexual debut among females is also similar (~16 years) [28]. As expected, prior studies in these countries have reported similar vaccine effectiveness against HPV-related diseases, including against cervical cancer in Sweden and Denmark, i.e., 88% and 86% effectiveness among females who were vaccinated at <17 years of age, respectively [20] [21]. Also, in a very recent Norwegian analysis focusing on Gardasil vaccine effectiveness against CIN2+, investigators reported 82% effectiveness among females vaccinated <17 years of age (lower compared with estimates above but expected given the higher attribution of HPV types other than 16 and 18 in cervical precancer versus cancer) [41].

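### The 80% power for 60 cases assumes one uniform 25% coverage, but matching in effect holds birth year fixed while Norwegian and Danish coverage before 17 runs from near zero to about 70% by birth cohort, so the stated power is optimistic

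*Protocol*

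**What the plan says.** Section 7.8 (Study Size) sets the power with "constant alpha-level of 0.05, control/case ratio of 10" and a single weighted coverage varied from 20% to 30%. The headline case reads "To detect a true OR of 3.0 with an overall vaccination coverage of 25% in all three countries combined", for which "approximately 60 AoRRP cases would be needed to achieve a power of at least 80" per cent. The success bound is an odds ratio of at least 3.0 "with a lower bound for the confidence interval of at least 1.33". The country figures behind the overall value "are ~20% for Sweden, ~50% for Denmark, and ~25% for Norway, and is expected to be at least 25% overall". The Abstract and Annex 1 repeat the 80% statement.

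Section 7.1 says: "Cases and controls will be matched on age (+/- 1 year) at diagnosis, calendar year, and the region where case was diagnosed". Section 7.11 keeps each case and her controls as a stratum of a conditional logistic regression.

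The Abstract describes the population as women "eligible for HPV vaccination at <17 years of age, i.e., birth cohorts 1990 and later", and Table 1 applies 1990 as the first birth year in all three countries. The programme history in Sections 5 and 7.1 differs by country:

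- **Norway:** the programme started in 2009, and "The first cohort targeted was girls born in 1997, with coverage >70" per cent.
- **Denmark:** catch-up at ages 13-15 began in October 2008, so from about births 1993. Coverage in targeted cohorts is above 70%.
- **Sweden:** partly subsidised vaccination at 13-17 from 2007, and a school programme for births from 1999.

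**The concern.** Age at diagnosis together with calendar year determines birth year to within about a year. A woman in a cohort with no programme is therefore compared almost only with women of that same cohort. If none of the 11 women in a set is vaccinated, the set drops out of the conditional likelihood. A country average of 25% made up of cohorts near 0% and cohorts near 70% behaves differently from 25% everywhere.

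Denmark and Norway were added to reach about 60 cases and 80% power. If many of the added cases sit in cohorts without a vaccination contrast, the case count overstates what was gained.

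A second, smaller leak concerns cases who were partly vaccinated, or first vaccinated at 17 or older. Under Sections 7.1 and 7.6.1 they are neither exposed nor unexposed in the primary comparison. The case estimates in Section 7.8 were made without vaccination status and so include them. Danish births 1990-1992 were about 20-22 years old when the 2012 catch-up to age 27 opened.

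**Working it through.** **Inputs from the protocol:** 60 cases, 10 controls per case, true odds ratio 3.0 (unvaccinated versus vaccinated), coverage 25%, lower bound 1.33 (Section 7.8); birth and calendar windows (Table 1); programme dates (Sections 5 and 7.1); 46 Swedish cases and fewer than 50 each in Denmark and Norway (Section 7.8). Coverage by birth cohort and the distribution of cases over cohorts are not given and are assumed below.

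**1. The plan's own figure.** In a set with m vaccinated women among 11, the case is the unvaccinated one with probability 3(11 − m) / [3(11 − m) + m]. Simulating this likelihood with a Wald 95% interval, 60 cases and uniform 25% coverage gives P(lower limit > 1) = 0.80 and P(lower limit ≥ 1.33) = 0.46 (0.45 in a repeat run). Table 2 states 0.80 for the 1.33 bound. So 0.80 matches exclusion of 1, not of 1.33. Other cells do not reproduce either way: for 40 and 80 cases the table has 0.67 and 0.87, against 0.56 and 0.92 (bound 1) or 0.24 and 0.60 (bound 1.33).

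**2. Empty sets under uniform 25% coverage.** P(case vaccinated) = 0.25 / (0.25 + 3 × 0.75) = 0.10. P(no one vaccinated) = 0.90 × 0.75^10 = 0.051, about 5%.

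**3. Share of cohorts without a described programme.** Count the years spent at ages 15-29 within 2006-2022 for each birth year.

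- Norway 1990-1996: 14 + 15 + 15 + 15 + 14 + 13 + 12 = 98. Norway 1997-2007: 11 + 10 + … + 1 = 66. Share 98/164 = 60%.
- Denmark 1990-1992: 14 + 15 + 15 = 44 of 164 = 27%.

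**4. Do the stated averages fit a two-level pattern?** Norway: 66/164 × 70% = 28% (stated about 25%). Denmark: 120/164 × 70% = 51% (stated about 50%). They do.

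**5. What two levels do to a set.** At zero coverage every set is empty. At 70%, P(case vaccinated) = 0.7 / (0.7 + 3 × 0.3) = 0.4375, and P(empty) = 0.5625 × 0.3^10 + 0.4375 × 0.7^10 = 0.012. Sets are nearly all empty or nearly all informative, depending on cohort.

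**6. Power at 60 cases, odds ratio 3.** Assumed coverage: Norway 0 before 1997, then 70%; Denmark 0 before 1993, then 70%; Sweden 0 for 1990, then 22%. Cases are spread over birth years by person-time times expected risk, with flat incidence by age. Each cell gives the share of empty sets / P(limit > 1) / P(limit ≥ 1.33).

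| Case mix SE/DK/NO | Average coverage | Exact birth-year match | Match within 1 year |
|---|---|---|---|
| Uniform | 25% | 5% / 0.80 / 0.46 | – |
| 46/7/7 | 24.5% | 27% / 0.68 / 0.38 | 20% / 0.73 / 0.40 |
| 20/20/20 | 33.1% | 44% / 0.73 / 0.45 | 35% / 0.75 / 0.46 |
| In proportion 46/49/49 | 33.4% | 45% / 0.73 / 0.45 | 36% / 0.76 / 0.48 |

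**7. Sensitivity of these results.**

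- A 3% floor for vaccination outside a programme, with matching within 1 year, gives 16% / 0.74 / 0.41 for 46/7/7 and 26% / 0.78 / 0.49 for 20/20/20.
- Incidence rising 1:2:3 over ages 15-19, 20-24 and 25-29, with exact matching, gives 30% / 0.65 / 0.35 for 46/7/7 and 49% / 0.66 / 0.40 for 20/20/20.
- Graded Swedish coverage of 2%, 15% and 55% for births 1990-92, 1993-98 and 1999+ (with Norway 0.5%, 72% and 2% for births 1990-96, 1997-2004 and 2005+, and Denmark 5% then 70%), mix 30/12/18, exact matching, gives about 45% / 0.65 / 0.38.
- The least favourable run (graded Swedish rollout, 46/7/7, rising incidence) gives 51% / 0.50 / 0.26. Its average coverage is only 21%, so part of that fall is lower coverage and not clustering.

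**The case against.** The strongest objection is that the protocol gives no coverage by birth cohort, so no share of empty sets can be derived from it. This stands, and it is why the result is a range. A reader might infer that nearly half of the 60 sets are certain to be empty. The documents do not support that as a fixed figure. With the patterns assumed here it needs exact birth-year matching and near-zero coverage outside programmes, and usually either a case mix with many Danish and Norwegian cases or a late, graded Swedish rollout. The protocol matches within a year, reports 46 Swedish cases, describes partly subsidised Swedish vaccination from 2007, and lists vaccines bought at own cost among the Danish data.

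A second objection is that counting empty sets overstates the loss. This also stands. Sets from cohorts at about 70% coverage are individually more informative than sets at 25%. With the 46/49/49 mix, 45% of sets are empty, yet power at the 1.33 bound is 0.45 against 0.46. That comparison is helped by average coverage of about 33%: uniform coverage of 30% or 35% would give 0.55 or 0.63 at that bound. At the protocol's own premise of about 25% (the 46/7/7 row), the loss is 0.06-0.08 at 1.33 and 0.07-0.12 at 1.

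Third, Section 7.8 expects more than 60 cases and coverage of at least 25%, so 60 at 25% is a threshold and not a forecast. True, but the threshold is what the 80% statement is attached to.

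Finally, a reader might infer that the early cohorts should not have been called eligible, or that keeping them biases the estimate. Section 7.2 defines eligibility as a chance of vaccination before 17, and Gardasil was available from 2006. Sets without a vaccinated woman add no information and no bias.

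**Conclusion.** The point holds as a moderate overstatement of power. One uniform coverage is used for an analysis that in effect compares women within birth cohorts, and the protocol's own programme dates and country averages point to near-zero and roughly 70% cohorts in Norway and, to a lesser degree, Denmark. Roughly 15-50% of 60 sets would be uninformative, against about 5% under the uniform assumption. Power to exclude 1 is roughly 0.64-0.78 in place of 0.80. At the actual bound of 1.33 it is about 0.35-0.49 against about 0.45, a loss of 0 to about 0.1. A late Swedish rollout combined with incidence rising with age can take both figures lower.

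These figures rest on assumed cohort coverage, case mix, age pattern and matching tolerance. The effect of cases partly vaccinated or first vaccinated at 17 or older comes on top and is not quantified here. The larger gap in Table 2, 0.80 stated against about 0.46 at 1.33 even with uniform coverage, is a separate matter that the same recalculation would settle.

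**What to change.** Recompute Table 2 by simulating the matched conditional analysis with coverage by country and birth year, the expected distribution of cases over countries and cohorts, the matching tolerance in Section 7.1, and the stated success criterion. Restate the 80% claim accordingly in the Abstract, Section 7.8 and Annex 1.

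Beside the case count, report the expected number of exposure-discordant sets. Leave out of the power count those cases who were partly vaccinated or first vaccinated at 17 or older, since they belong to neither comparison group. The 1990+ birth cohort may stay as it is.

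The cost is one simulation, cohort-level coverage figures from the registries, and revised text. Data collection and the primary model do not change. The downside is a less favourable stated power.
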